5.5.6 Safety Assessments

Safety assessments will consist of serious adverse events, adverse events, EKG tests, and safety laboratory measurements in the NCG vs. the PLBO group.

5.6 Treatment Compliance

Treatment logs will capture the timing and dosage of each occurrence of study drug administration. All treatments will be administered in the hospital so non-compliance with the medication is not a concern.

5.7 Study Termination/Stopping Rules

The study PI and Coordinating Center will seek input from the DSMB regarding the need to stop the study if either of the following events occurs: (a) Life-threatening adverse event that is clearly associated with drug hypersensitivity and/or (b) Unexplained serious illness or death of one of the participants.

The NIH and local IRBs (at their local site) or the site PI has the authority to stop or suspend this trial at any time. The Medical Monitor, DSMB, or FDA may recommend suspending or stopping the trial after a thorough review, due to evidence related to safety or efficacy based on planned interim analyses (see Section 7 on Safety Monitoring and Section 8.3.1 on Interim Analysis).

5.8 Subject Discontinuation

A subject will be discontinued from the study if s/he:

- Is determined not to have PA, MMA, CPSD, or OTCD (as defined in Section 5.1.1.1)
- Voluntarily withdraws or is voluntarily withdrawn from the study by his/her parents

The study drug will also be discontinued if a subject:

- Experiences a serious adverse event, deemed by the Medical Monitor and site PI to be related to or likely related to study drug administration.
- Has received a hepatic transplantation
- Relocates to a location, not within the catchment area of one of the other participating institutions

If a participant drops from the study before its completion, a narrative description of the reason(s) for discontinuation will be recorded on the Study Closeout Form (see Manual of Procedures).

5.9 Blinding

This is a double-blind, placebo-controlled trial performed in children's hospitals across the country. Handling, storage, dispensing, and record keeping of all study medication will follow a Pharmacy Manual, which will be developed by the Central Research Pharmacy at Children's National Hospital. The Pharmacy Manual will define the responsibilities and procedures of the Central Research Pharmacy and of the Site Pharmacies both of which will be unblinded.

5.9.1 Type of Blinding

The participants, their families, caregivers, and all research personnel at the sites, as well as the study chair and co-chair, will be blinded to the identity of the drug (NCG or PLBO). The appearance of active and placebo tablets is nearly identical.

5.9.2 Maintenance of Blinding

- NCG and PLBO will be sent to each site pharmacy by the Central Pharmacy (CNMC).

Short-Term Outcome of NCG in Hyperammonemia

- Assigned NCG/PLBO doses will be prepared individually for each subject by the Site Pharmacy.
- Identically labeled NCG/PLBO doses prepared by the Site Pharmacy will be dispensed by blinded hospital staff based on a prescription from the blinded study physician.
- An additional supply of NCG/PLBO will be provided as needed based on each site's enrollment rate to provide the doses of study medication for all newly enrolled subjects as well as a small supply to meet emergency needs at each site.
- The individual Site Pharmacy will prepare, blind and dispense unit doses of study medication for each enrolled subject from the drug supply while the subject is hospitalized.
- All unopened medications will be stored at controlled refrigerated temperature (2-8° C; 36-46° F), and opened medications will be stored at controlled room temperature (15-30° C; 59-86° F) in a secure area in the site's research pharmacy to which access will be limited to the research pharmacist and designated assistants. To maintain blinding, only the site pharmacist and designated assistants will have access to the secured area.

5.9.3 Breaking the Blinding

Treatment assignment should not be unblinded unless the Medical Monitor assesses that knowledge of drug assignment is required in order to assess how to treat a safety concern within a patient. The site investigator should contact the Coordinating Center immediately if he/she believes that knowledge of the treatment assignment will affect their decision regarding treatment of a safety concern.

6 STUDY TREATMENTS

6.1 Study Intervention

Carbaglu® 200 mg Dispersible Tablets (N-carbamylglutamate), scored in three places, allowing each tablet to be broken into four 50 mg pieces.

The target dose is 150 mg/kg/d for patients \leq 15kg or 3.3 g/m²/day for patients $>$ 15kg, divided into two equal doses 12 hours apart. Each dose will be rounded to the nearest 50mg using the dosing nomograms provided. The maximum variance from the calculated target daily dose and the actual daily dose will be 23.5% or less. Study drug will be prepared for administration according to the package insert. The suspension has a slightly acidic taste and a white, cloudy appearance. Participants will either receive PLBO or the study intervention, NCG (Carbaglu®) 150 mg/kg/day for patients \leq 15kg or 3.3 g/m²/day for patients $>$ 15 kg.

6.2 Control (Placebo) Intervention

The placebo and NCG tablets, which are produced by the same manufacturer and include the same inactive components look and taste similar. When the two tablets are suspended in solution, there is a slight difference in a hue that is only distinguishable when the two solutions are observed side by side.

6.3 Dispensing of Study Medications

- Handling, storage, dispensing, and record keeping of all study medication will follow a Pharmacy Manual, which will be developed by the Central Research Pharmacy (CRP) at the Children's National Hospital. The CRP Pharmacy Manual will define the responsibilities and procedures of the CRP and of the site pharmacies both of which will be unblinded.
- The CRP will receive study medication (NCG) and matched placebo (PLBO) from Orphan Europe.
- Once the CRP and the Coordinating Center at Children's National Hospital determine a site pharmacy is appropriately certified and ready to receive the drug, the CRP will ship an initial quantity of NCG and PLBO to the individual site research pharmacy.
- All doses of NCG/PLBO (as assigned) will be prepared, blinded, and dispensed in unit doses individually for each subject by each site pharmacy while the subject is hospitalized.

6.4 Provisions for Access to Investigational Treatment after Study

The results of the study will be shared with the patient, his/her family, and his/her treating physician. If the study reveals that NCG is effective, the treating physician will have the prerogative for treating the patient off-label with NCG, which is already approved for use in NAGS deficiency, until it is approved by the FDA for additional indications.

6.5 Drug Packaging/Handling/Storage/Accountability

- Oral NCG and matching PLBO will be supplied by Orphan Europe and distributed to each site by the CRP
- The designated research pharmacist, investigator, or coordinator at each participating site will be required to acknowledge receipt of study drug shipments/doses and notify the CRP of any problems with shipments or with the on-site supply of study medication.

Short-Term Outcome of NCG in Hyperammonemia

- S/he will sign receipts for medication supplies, which will be kept in a secure area in the site's research pharmacy to which access will be limited to the research pharmacist and their designated assistants. To maintain blinding, only the site pharmacist and designated assistants will have access to the secured area.
- Unopened bottles of medications will be stored at controlled refrigerated temperatures (2-8° C; 36-46° F).
- Opened bottles of medications will be stored at controlled room temperature (15-30° C; 59-86° F). The date of first opening a bottle will be recorded on the tablet container.
- Drug accountability logs will be completed by the site pharmacists and the study coordinators.
- The sites will update their monthly supplies logs and expiration dates and the information will be monitored by the central pharmacy.
- Unopened bottles of medications will not be used after the expiration date stated on the tablet container. Opened containers of medications will not be used after 30 days of first opening.
- All unused study medication will be returned by the site to the central pharmacy and be documented in the study database. After reconciliation, the drug will be destroyed or retained and used in animal research.
- At the conclusion of the study or as required for review, supplies of received, dispensed and returned medication will be reconciled to account for all distributed supplies of PLBO/NCG.

6.6 Concomitant Therapy

6.6.1 Therapies Prohibited Before/During the Trial

All investigational drugs, biologics, and therapies are prohibited following enrollment in this trial.

This includes the use of alternative pathway medications, including sodium benzoate, and any medication with phenylacetate as an active metabolite (e.g., Buphenyl, Ammonul, Ravicti) in propionic acidemia, and methylmalonic acidemia; these medications have not been approved for this indication and there is no evidence for their effectiveness in these conditions.

No other changes in the special diet or medications are called for in this protocol.

6.6.2 Therapies Allowed During the Trial

Standard therapy, including but not limited to intravenous fluids, dextrose, intralipids, biotin, hydroxocobalamin, levocarnitine, metronidazole, and metabolic specialty formulas. Hemodialysis or hemofiltration may be administered as determined by the treating physician.

In CPSD and OTCD, FDA approved alternative pathway medications (e.g., Na-benzoate, Na-phenylacetate, Buphenyl, Ammonul, Ravicti) are allowed and are indicated in these conditions.

7 SAFETY MONITORING

The study protocol will be submitted to the FDA under IND # 68,185 and will be reviewed by the study DSMB (Section 7.2) and the Medical Monitor (Section 7.3). Participant enrollment may only begin after final IRB approval.

7.1 Adverse Events (AEs)

7.1.1 Definitions

7.1.1.1 Adverse Event and Suspected Adverse Reaction

As defined in title 21 of the Code of Federal Regulations Part 312, an *adverse event (AE)* is "any untoward medical occurrence associated with the use of a drug, whether or not considered drug related". All adverse events will be classified using version 4.0 of Common Terminology Criteria for Adverse Events (CTCAE), developed and maintained by CTEP at the National Cancer Institute (<http://evs.nci.nih.gov/ftp1/CTCAE/About.html>).

A *suspected adverse reaction* is any adverse event for which there is a reasonable possibility that the drug (NCG) caused the adverse event. "Reasonable possibility" means that there is evidence, such as a temporal relationship, to suggest a causal relationship between administration of NCG and the adverse events. It is less certain about causality than *adverse reaction*.

7.1.1.2 Serious Adverse Events

Title 21 of the CFR also provides a definition for serious adverse events (SAEs), described as those events that result in death; or are life-threatening; or require prolonged inpatient hospitalization or prolongation of existing hospitalization, or create persistent or significant disability/incapacity, or a congenital anomaly/birth defects. However, application of this definition is difficult in subjects who, because of their underlying congenital disorder, present with a life-threatening illness, requiring lengthy inpatient hospitalization.

Administration of NCG has not been described to result in serious adverse events (see side effects section 1.3.4), and using the standard definition of SAEs is likely to result in capture of events secondary to the underlying acute metabolic disease, and which would not be helpful in the collection of data pertaining to NCG or its administration. Therefore, for this study, we modify the standard definition and define **serious adverse events as those events that:**

- Result in death
- Are life-threatening, that is, places the patient at immediate risk of death from the event as it occurred. Because acutely ill patients with PA or MMA are likely to experience life-threatening events as part of their underlying condition and meeting eligibility criteria, this category will be restricted to events that arise as new events subsequent to administration of NCG, not having started prior to administration of NCG. Life-threatening events resulting from processes, which based on the opinion of the investigator likely began prior to administration of NCG but had not been identified because the diagnostic investigation had not yet been performed, will not be considered serious adverse events.

- Require prolongation of existing hospitalization. This category will be restricted to only complications that clearly extend the hospitalization that was anticipated at randomization to an episode.

Serious Adverse Events in between episodes

- Result in death
- Are life-threatening
- Require hospitalization (except for elective hospitalizations for e.g. elective procedures and hospitalizations for a hyperammonemic event which are episodes and not SAEs)
- Note: if a hospitalization occurred without an episode-qualifying ammonia level, but later in the course of the hospitalization, the ammonia level rises to a qualifying episode, the participant will be randomized to treatment and the hospitalization will **not** be considered an SAE.
- Cause prolongation of existing hospitalization
- Cause persistent or significant disability/incapacity
- Cause a congenital anomaly/birth defects

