1.3.4 Safety and Side Effects of Carbaglu

The safety of Carbaglu for the treatment of hyperammonemia due to NAGS deficiency was evaluated in a retrospective review of 23 patients (14 males and 9 females) (Carbaglu [prescribing information]. Orphan Europe; 2010). The most common adverse reactions (occurring in $\geq 13\%$ of patients), regardless of causality, were infections, vomiting, abdominal pain, pyrexia, tonsilitis, anemia, ear infection, diarrhea, nasopharyngitis, and headache.

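### The in-episode SAE list omits disability, excludes life-threatening worsening of pre-dose processes, gives no way to record the expected stay, and conflicts with Section 2.2

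*Combined protocol and SAP*

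**What the plan says.** Section 7.1.1.2 first cites the federal definition, which covers events that "create persistent or significant disability/incapacity, or a congenital anomaly/birth defects" as well as death, threat to life and prolonged stay. It then says "for this study, we modify the standard definition and define" and gives three items:

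- death, without restriction;
- life-threatening events, "restricted to events that arise as new events subsequent to administration of NCG, not having started prior to administration of NCG". Processes that in the investigator's opinion "likely began prior to administration of NCG but had not been identified because the diagnostic investigation had not yet been performed" are also excluded;
- prolonged stay, limited to "only complications that clearly extend the hospitalization that was anticipated at randomization to an episode".

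The reason given is that the standard definition would mostly capture the underlying metabolic illness.

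A second list in the same section, headed as applying between episodes, puts no new-event limit on life-threatening events and includes "Cause persistent or significant disability/incapacity".

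Section 2.2 makes the SAE rate during episodes the primary safety outcome. It defines those SAEs as death or a substantially longer stay and names nothing else.

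**The concern.** The narrower list applies while study drug is being given, and the fuller list applies when it is not. The section's general reason, disease noise, does not explain why disability is dropped within episodes and kept between them.

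Several safeguards hang on the SAE label. They are the 24-hour site report (7.1.2.1), causality assessment by the Medical Monitor as well as the site (7.1.2), the criterion in 5.8 for discontinuing study drug after a related SAE, and the tabulation of events by seriousness (8.1.2). An event that misses the label misses these safeguards or is counted in the wrong category.

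The prolongation item adds a judgement that may be made after the outcome is known. The disagreement between 2.2 and 7.1.1.2 leaves the content of the primary safety outcome undetermined.

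**Working it through.** The plan states no figure for this point, so the check compares texts.

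**Step 1. The definitions side by side.**

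| Criterion | Standard, as cited in 7.1.1.2 | In-episode list, 7.1.1.2 | Between-episode list, 7.1.1.2 | Section 2.2 |
|---|---|---|---|---|
| Death | yes | yes | yes | yes |
| Life-threatening | yes | only if new after dosing | yes | not named |
| Longer stay | yes | only if clearly beyond the stay expected at randomization | yes | only if substantial |
| Disability | yes | absent | yes | not named |
| Congenital anomaly | yes | absent | yes | not named |

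The in-episode list has no heading of its own. That it governs treated episodes is inferred from the heading of the second list and from Section 2.2.

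**Step 2. Four cases run through the definitions.**

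| Event during a treated episode | Standard | 7.1.1.2, in-episode | 2.2 |
|---|---|---|---|
| A. New injury, lasting disability, no threat to life, no extra days | SAE | not SAE | not SAE |
| B. Process present before dosing becomes life-threatening on drug; patient survives; stay not extended | SAE | not SAE | not SAE |
| C. As B, but fatal or clearly extending the stay | SAE | SAE | SAE if fatal or if the extension is substantial |
| D. New life-threatening event after dosing; resolves; stay not extended | SAE | SAE | not SAE |

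Case A shows the disability gap. Cases B and C show the true reach of the new-event limit: it sits only inside the life-threatening item. Section 5.4.1 requires ammonia of at least 70 µmol/L, so hyperammonemia itself always predates dosing and its worsening falls under B or C. The limit is argued from PA and MMA but worded to cover CPSD and OTCD as well. Case D shows the contradiction: the same event is an SAE in one section and outside the primary safety outcome in the other. The prolongation wording also differs, since 7.1.1.2 asks for clarity and 2.2 for size.

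**Step 3. Is the expected stay recorded?** Section 5.4.1.2 and Table 1 list ammonia, amino acids, safety laboratory tests, pregnancy test, EKG and Functional Status Scale. Table 1 and 5.4.1.3 add treatment, concomitant-medication, transfusion and adverse-event logs. None holds an expected stay or discharge date.

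**Step 4. Scale, for context only.** The target is 114 episodes (8.4). Assuming 1:1 allocation, 114/2 = 57 are on NCG. Treating episodes as independent:

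- No recorded SAE of a given type gives an upper 95% bound of 1 − 0.05^(1/57) = 5.1% per episode.
- A harm with a true rate of 1%, 2% or 5% per episode occurs at least once with probability 1 − 0.99^57 = 44%, 1 − 0.98^57 = 68% or 1 − 0.95^57 = 95%.
- One or two events are 1/57 = 1.8% or 2/57 = 3.5% of NCG episodes.

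These figures show that single labels matter at this size. They do not estimate how many would be wrong.

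**The case against.** The sponsor can fairly say that the narrowing is deliberate and reasoned. These patients arrive acutely ill, and randomization balances disease events only in expectation, which does little for case-by-case review. The new-event limit is therefore a defensible trade-off. That stands, and the point does not rest on removing the limit.

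The sponsor can also point to other safeguards. All adverse events are collected daily, graded and sent to the DSMB in aggregate (7.1.2). The DSMB is to be told at once of life-threatening events, with no new-event limit in that sentence (7.2). Unexplained serious illness prompts DSMB input (5.7). Function is scored daily and events are compared by arm. These stand too, but the only expedited route described from site to coordinating center is for SAEs.

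Four stronger readings are tempting and are not supported:

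- *All worsening of pre-dose processes is dropped.* Case C shows otherwise.
- *The expected stay is never recorded.* The eCRFs and Manual of Procedures are not among the documents, so one can say only that no recording procedure is described.
- *Expedited FDA reports are widely lost.* Those require an unexpected event as well (7.1.2.1), and 7.1.1.3 treats the disease spectrum, including pancreatitis and cardiomyopathy in PA, as expected.
- *The thin prior safety base measures the problem.* Section 1.3.4 lists reactions in at least 13% of 23 patients (0.13 × 23 = 2.99, so 3 patients), and rarer events need not appear there. That weakens the appeal to past experience but says nothing about how many events would be mislabelled.

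**Conclusion.** The concern holds in limited form. Two kinds of serious on-drug event can be classed as non-serious: new lasting disability without a longer stay, and life-threatening worsening of a process begun, or judged likely to have begun, before dosing that neither kills nor clearly extends the stay. Prolongation lacks a described baseline and may be judged in hindsight. What is lost is expedited handling, routine Medical Monitor causality review, the SAE-based discontinuation trigger and correct classification by seriousness. A reader might infer that these harms vanish from the trial, but aggregate reporting to the DSMB rules that out.

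The disability and recording gaps are cheap improvements. The disagreement between 2.2 and 7.1.1.2 is wrong as written. While it stands, adding disability to 7.1.1.2 would not change the primary safety rate as 2.2 defines it.

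The number of affected events cannot be derived from the documents. The conclusion assumes that the unheaded list governs treated episodes and that no unseen form captures the expected stay.

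**What to change.** 1. Add the disability criterion to the in-episode list, in the terms of the between-episode list ("Cause persistent or significant disability/incapacity").
2. Add an expected discharge date to the randomization eCRF, entered before the first dose, and judge prolongation against it. Flag earlier episodes that were judged without it.
3. Reconcile Section 2.2 with both lists in 7.1.1.2, so that one in-episode definition governs reporting and the primary safety outcome, with one wording for prolongation.
4. Optionally, tabulate by arm, as a separate category, life-threatening worsening of processes present before dosing, leaving the SAE limit unchanged.

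The cost is amendment wording, one eCRF field and somewhat more SAE reports. Section 9.10 requires approval by the DSMB and the lead IRBs, then by each site IRB. The study was activated in July 2012 and Section 8.3 shows that episodes had already accrued, so the expected date will exist only for episodes after the amendment. The discontinuation criterion in 5.8 refers to SAEs, so a wider definition widens its reach; the sponsor should confirm that the two sections still agree.

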7.1.1.3 Expected and Unexpected Adverse Events

An unexpected adverse event or reaction is defined as any adverse experience, the specificity or severity of which is not consistent with the risks described in the protocol (see Section 1.3.4 on Safety and Side Effects of Carbaglu) or in the Carbaglu investigator's brochure. Expected adverse events are those that are identified in the research protocol as having been previously associated with or having the potential to arise as a consequence of participation in the study or are part of the clinical spectrum of the underlying disorder. Common acute and chronic complications of propionic and methylmalonic acidemia include:

- Anorexia
- Vomiting
- Lethargy
- Stupor
- Coma
- Seizures
- Ketosis
- Acidosis
- Hyperventilation
- Hyperglycemia
- Hypoglycemia
- Hypothermia
- Neutropenia; bone marrow suppression
- Electrolytes abnormalities
- Amino acid abnormalities
- Pancreatitis (PA)
- Renal dysfunction (MMA)
- Cardiomyopathy (PA)

